9.1 Baseline Data Analysis

The baseline data analysis will involve the following components.

9.1.1 Compare the characteristics of respondents in the treatment and comparison groups. This will include a description of respondents by age, gender, household composition, marital status, residential status, level of education, current work situation, financial status and ethnicity. The purpose of this analysis is to provide an indication of the ‘match’ in socio-economic characteristics between the treatment and comparison groups. In addition, the analysis will position both groups relative to the population as a whole, using comparative data from the Growing up in Ireland (GUI) study. As the GUI study is deemed to be nationally representative, and the NEYAI is targeted towards relatively disadvantaged communities, the analysis will also assess the extent of targeting. It is recognised that the interpretation of this data will need to be done with some care and take account of the different times when the data was collected (2007/9 for GUI data, 2011/13 for NEYAI

103 Request for Tender For Evaluation of National Early Years Access Initiative, 2011.

data) and the limitations this may place in drawing comparisons¹⁰⁴. The data will be presented in simple tables and bar charts based on group means and standard deviations. It is recognised that whether or not the treatment and comparison groups are well-matched or poorly-matched will not affect our ability to identify the impact of NEYAI – since all *measured* sources of variability can be statistically controlled – but it may be useful to know if there are systematic variations in target group characteristics either between the two groups or within the treatment group.

9.1.2 Construction of multivariate outcome measures. The outcomes of the initiative, as shown in the logic model in Figure 1, are improved child and parent outcomes. The logic model also shows intermediate outcomes, notably improved staff capacity, which may act as a pathway to final outcomes. These outcomes are latent variables in the sense that each of them is based on an underlying construct which is manifested through various ‘proxies’ or ‘indicators’. This is illustrated in Figure 2 above and shows how child and parent well-being are latent variables which manifest through, and are measured by, a range of indicators; that is why the arrows point from the latent variable to the indicators which measure it. Detailed analysis will be undertaken to construct robust latent variables for all outcome measures and establish their validity (both discriminant and convergent). There are many precedents for measuring child and parent outcomes in this way but the measurement of staff capacity, particularly in the childcare sector, is more novel and will require a more exploratory approach. This part of the analysis, which establishes the ‘measurement models’ for the evaluation, is a crucial building block for the subsequent analysis, and is effectively a test of the conceptual framework underpinning each of the questionnaires as illustrated in Figures 3, 4 and 5 above.

9.1.3 Construct a model of child and parent well-being. This will build on the ‘measurement model’ just described and analyse how the latent variables relate to each other. The resulting ‘structural model’ will combine the measurements of child and parent well-being with all possible influences within the dataset to produce an overall model, somewhat similar to the model described in Figure 2 above. The analysis will distinguish between an ‘optimal’ model, which utilises the NEYAI dataset only, and a ‘comparison’ model based on those concepts shared between NEYAI and GUI. The rationale for this is that GUI has less data on parental well-being compared to NEYAI and this may influence the resulting models of child and parent well-being. The results of this analysis will allow us to compare key outcome measures between the two datasets and thus allow us to position the NEYAI sample relative to the national GUI sample.

104 For example, the impact of the recession, which began to manifest in 2008 and has deepened since then, will need to be considered and we will draw upon our cross-sectional analysis of the baseline data to form a view as to the importance of economic factors relative to other influences on the key benchmark indicators.

9.1.4 Construct a model of staff capacity. This involves using the same analytical approach described in the previous paragraph – excluding GUI data which does not cover this topic – and will test the underlying concept of staff capacity, and its determinants, as hypothesised in Figure 5 above.

9.1.5 Generate descriptive data on the treatment and comparison groups, based on variables identified in the multi-level models as having a significant role in either defining or determining outcomes. This approach to descriptive data has the merit of ensuring that data is generated on the basis of what has already been shown to be significant in the overall analysis of outcomes rather than simply producing descriptive statistics ‘for the sake of it’. As a consequence, this approach avoids the danger of over-producing descriptive data which, on subsequent analysis, turns out to be irrelevant. Table 2 is a possible format for presenting these descriptive statistics.

Table 2 Format for Presenting Descriptive Statistics in the Interim Report

Var- iable	Mean & Standard Deviation Scores for Treatment Group (TG)												Mean & Standard Deviation Scores Comparison Group (CG)										GUI Score	
	BC	CC	CK	CN	DD	DL	FL	LD	LK	RO	TT	All	1	2	3	4	5	6	7	9	10	All		
*																								
**																								

*Denotes a statistically significant difference between treatment group and comparison group for that variable.

**Denotes a statistically significant difference between treatment group or comparison group and the GUI for that variable.

9.1.6 The results of the foregoing analysis will be presented and interpreted in the Interim Report. This will also include a Technical Appendix giving the detailed statistical results.

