4.3 Does NEYAI have an impact?

We propose a quasi-experimental design⁴⁷ since, in the circumstances, this is the most appropriate way of answering the first evaluation question: does NEYAI have an impact on children and their parents by comparison with a matched sample of those who have not participated in NEYAI? This design involves comparing the treatment group (those who receive the 'NEYAI treatment') with a comparison group (those who receive the 'usual treatment'), both groups matched in terms of demographic and socio-economic characteristics. More specifically, this design involves three related elements:

- (i) assessing the treatment group at baseline (before the NEYAI intervention) and at follow-up (immediately after the NEYAI intervention) in order to measure any changes in the intervening period;
- (ii) assessing a matched comparison group at baseline (without any intervention other than 'treatment as usual') and at follow-up (using the same intervention period as the treatment group) in order to measure any changes in the intervening period;
- (iii) comparing changes in the treatment group and the comparison group in order to establish the difference in outcomes between NEYAI intervention and 'treatment as usual', thereby measuring the *net* impact of the intervention.

The measurement of difference in outcomes between the treatment and comparison groups - 'between-group differences' - is an acceptable and accepted way of measuring impact provided that all of the measured differences between the two groups are taken into account. However it also needs to be recognised that it is not a perfect comparison since, due to the absence of randomisation⁴⁸, there may be unmeasured differences between the two groups which could account for any difference in the observed net impact. The perfect comparison involves an experimental design, usually called a randomised control trial (RCT), but this is not an option since the NEYAI was not designed with that in mind and, moreover, could be difficult to design in practice. Nevertheless, the quasi-experimental method provides an important degree of confidence that,

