47 A quasi-experimental method involves setting up two groups (an treatment and comparison group) except that the process of random allocation is not used to establish each group, either because of ethical or practical considerations, or both. In the case of NEYAI, the reasons are entirely practical due to the design of the programme which effectively rules out the possibility of random allocation. The absence of random allocation means that it is not possible to be sure that the treatment and comparison groups are perfectly matched. Nevertheless, when both groups are matched on a range of measured variables – bearing in mind that, due to the absence of random allocation, there is no control over unmeasured variables - it may be reasonable to infer that differences between the treatment and comparison groups are attributable to the programme. In this way, the quasi-experimental method is sometimes regarded as an appropriate test of a programme, even if second best to a randomised control trial. Where a comparison group is not possible, the use of advanced statistical techniques to control for the separate influence of each variable in the dataset is a useful alternative except that it cannot control for the influence of participating in a programme versus not participating.

48 The effect of randomisation is to ensure that both groups are matched on measured as well as unmeasured characteristics.

where net impacts are detected, they are more likely to have occurred as a result of NEYAI rather than by chance.

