5.2 Comparison Group Sample

The comparison group sample is created in three stages. First, the catchment areas of the treatment group are identified in terms of demographic and socio-economic characteristics. For each NEYAI project, its catchment area is defined as the sum of the catchment areas of each childcare centre participating in the evaluation.

The data used to define these catchment areas is derived from the 2006 Census of Population, based on 'Small Areas' which have a minimum of 65 households and an average of 100 households; as such the data is almost 'street-level' and allows catchment areas to be defined precisely. This data will be expressed in terms of its deprivation score using the Pobal-Haase Index⁷². This data has the advantage that it is immediately available and, more to the point, the only data that allows areas to be defined in this way. The disadvantage is that while it is possible to match treatment and comparison areas in terms of deprivation scores, it is not possible to match them on other family characteristics which may be more relevant to this evaluation such as child and parent well-being, family functioning, neighbourhood and community factors. Nevertheless, the use of deprivation scores is the best available option and there are precedents for drawing comparison groups in this way, a notable example being the Sure Start evaluation⁷³.

Second, having established the level of deprivation in these catchment areas, a set of comparison areas will be identified which are matched as closely as possible to the treatment areas. In each of these comparison areas, childcare centres will be drawn from the Pobal database to match the

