73 The first phase of the National Evaluation of Sure Start Impact Study compared children/families in 150 of the first 260 SSLP [Sure Start Local Programmes] with their counterparts living in 50 communities that did not have up-and-running SSLPs at the time they were studied but which were to have programmes shortly after data collection (that is, Sure Start-to-be communities). 'Overall data were collected on 12,575 nine-month-olds and 3,927 36-month-olds and their families in 150 SSLP communities, and on 1,509 nine-month-olds and 1,101 36-month-olds and their families in the comparison communities' (Belsky and Melhuish, 2007:136-137). In a subsequent follow-up, a sub-sample of the children in SSLP areas were compared to a sample of children from the Millennium Cohort Study (MCS) not living in SSLP areas. Propensity scoring was used to estimate if there was a significant difference between the two sets of areas in terms of '85 indices of deprivation and other areas characteristics obtained from administrative sources' (National Evaluation of Sure Start Team, 2010:11). The results of this analysis revealed that 'SSLP populations were, in general, more disadvantaged than the comparison population drawn from the MSC sample', and this in turn, 'posed problems in making comparisons between roughly equivalent NESS and MSC groups in order to evaluate the putative SSLP effects' (Ibid). The creation of a comparison group for the NEYAI evaluation is unlikely to generate such challenges because we expect to be able to find comparison areas that are a close match of treatment areas on the Pobal-Haase Index.

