childcare centres in the treatment group⁷⁴. The comparison group therefore is taken to represent the 'usual', 'average' or 'conventional' treatment provided by childcare centres to children and their parents. In other words, the basis of comparison in this evaluation is 'NEYAI treatment' versus 'treatment as usual' rather than 'NEYAI treatment' versus 'no treatment'. This also means that we explicitly exclude areas from the comparison group where it is known that other intensive childcare initiatives are operating such as Ballymun, Coolock and West Tallaght where there is already a significantly-above-average investment in early years programmes. This approach is reasonable and, in the circumstances, the best option available but it also needs to be acknowledged that 'treatment as usual' is an umbrella term which conceals more than it reveals since we do not know what 'usual treatment' actually means or how much it varies within as well as between childcare centres.

Third, the evaluators in collaboration with Pobal, will approach the City/County Childcare Committees and/or Partnership Companies in the identified areas and invite them to participate in the study. If agreeable, they will be asked to nominate someone who will act as a Study Coordinator in order to liaise with the selected childcare centres in their area. These Study Coordinators, whose role in the evaluation will be the same as the Project Coordinators in the treatment group, will be briefed by the evaluation team based on the same set of guidelines (see Appendix Two). Identical procedures will be used to select the sample of children.

The benefits to the City/County Childcare Committees and/or Partnership Companies of participating in this study are similar for those who are already participating in the NEYAI – excluding the benefit of implementing an NEYAI project - since each will receive study results for their area and will participate in a broader national study of childcare. Our expectation is that this benefit, in conjunction with the support of Pobal, will be sufficient to ensure their willingness to participate in the study and to adhere to its requirements.

6. Measurement Instruments

The dataset for the evaluation is generated through the following linked set of measurements:

- ✓ Child Questionnaire
- ✓ Parent Questionnaire
- ✓ Staff Questionnaire
- ✓ Template for describing each project intervention in the evaluation
- ✓ Data extraction on project area characteristics

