Name of Project	Have you been in contact with this project in the period between this and the last meeting of the Learning Community?	If yes, about how many times have you been in contact?
BC Early Years Language & Learning Initiative, Ballyfermot / Chapelizod	 ₁ Yes  ₂ No  ₃ Not Applicable if this is your project	
CC Bringing It All Back Home, Canal Communities	 ₁ Yes  ₂ No  ₃ Not Applicable if this is your project	
CK Happy Talk Project, Cork	 ₁ Yes  ₂ No  ₃ Not Applicable if this is your project	
CN Addressing Gaps in Training & Practice, Clondalkin	 ₁ Yes  ₂ No  ₃ Not Applicable if this is your project	
DD Early Years Numeracy Project, Dublin Docklands	 ₁ Yes  ₂ No  ₃ Not Applicable if this is your project	
FL Fingal Parents Initiative, Fingal	 ₁ Yes  ₂ No  ₃ Not Applicable if this is your project	
DL Professional Pedagogy Project, Donegal	 ₁ Yes  ₂ No  ₃ Not Applicable if this is your project	
LK Start Right, Limerick	 ₁ Yes  ₂ No  ₃ Not Applicable if this is your project	
LD Tus Nua, Longford	 ₁ Yes  ₂ No  ₃ Not Applicable if this is your project	
RO Dublin SW Inner City Demonstration Model, Rialto	 ₁ Yes  ₂ No  ₃ Not Applicable if this is your project	
TT Quality Through Professionalisation, Tallaght	 ₁ Yes  ₂ No  ₃ Not Applicable if this is your project	

In the period between this meeting and the last meeting of the Learning Community, have you attended any events such as conferences, seminars or training workshops about any aspect of your work or about the early years sector in general?

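### Section 9.1.1 wrongly says that poor matching cannot affect identification of impact, and areas with other intensive initiatives are removed from the comparison arm only

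*Protocol*

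**What the plan says.** Section 9.1.1 plans a comparison of respondents' demographic and socio-economic characteristics by group. It then states that whether the two groups are "well-matched or poorly-matched will not affect our ability to identify the impact of NEYAI". The reason given is that all measured sources of variability can be statistically controlled, with the word 'measured' emphasised.

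Section 4.3 says that, without randomisation, "there may be unmeasured differences between the two groups which could account for any difference in the observed net impact". Footnote 47 to that section adds that "there is no control over unmeasured variables".

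Section 5.2 matches areas on the Pobal-Haase deprivation score from the 2006 Census and concedes that "it is not possible to match them on other family characteristics which may be more relevant to this evaluation". Childcare centres are then drawn from the Pobal database to match the treatment centres, with no criteria given.

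Section 5.2 also states: "we explicitly exclude areas from the comparison group where it is known that other intensive childcare initiatives are operating". Ballymun, Coolock and West Tallaght are the examples. Section 5.1, which defines the treatment sample, has no such exclusion. Table 1 and Appendix Six list a treatment project in Tallaght: "TT Quality Through Professionalisation, Tallaght".

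**The concern.** There are two separate problems.

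The first is a stated inferential property that is wrong. The premise in 9.1.1 covers measured variables only, but the conclusion covers matching in general. A team that holds this view has no reason to act on a poor match. Yet baseline collection closes in October 2012 and the Interim Report is due in March 2013, before follow-up closes in June 2013, so there is time to respond.

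The second is an exclusion applied to one arm. If a treatment centre lies in an area with another intensive initiative, its children are compared with areas chosen to have none. The contrast is then NEYAI plus the other programme against usual care, and whatever the other programme adds to change between baseline and follow-up is counted as NEYAI impact.

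**Working it through.** **1. The plan's own figure.** Sections 4.5 and 5 give 11 projects × 35 = 385 per group, power 0.8, p = 0.05 and effects of 0.2 to 0.5. Assuming a two-sided test, SD 1, no clustering and no attrition:

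- SE = √(2/385) = 0.0721
- power at 0.2 = Φ(0.2/0.0721 − 1.96) = 0.792

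The plan's figure therefore reproduces at the lower end of its range. The point does not rest on it, but it sets the scale.

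**2. Unmeasured differences.** Section 9.1.1 says that matching quality does not affect identification. Section 4.3 says that unmeasured differences could account for the net impact, and footnote 47 says that they are not controlled. Matching affects unmeasured differences as well as measured ones, so the unqualified conclusion cannot stand beside 4.3. As an illustration, take no true effect and an assumed residual bias b. The chance of a significant result is Φ(b/SE − 1.96) + Φ(−b/SE − 1.96):

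| assumed b (SD) | chance of p < 0.05 |
|---|---|
| 0 | 5.0% |
| 0.05 | 10.7% |
| 0.10 | 28.4% |
| 0.15 | 54.8% |
| 0.20 | 79.2% |

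**3. Measured differences: two estimates diverge.** Sections 4.3 and 9.2.2 measure impact by comparing change from baseline to follow-up. Section 9.2.3 uses coefficients that control for other variables and does not say whether baseline outcome is one of them. Let D0 and D1 be the group differences at baseline and follow-up, with equal SDs and pre-post correlation r.

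- Change comparison: D1 − D0
- Baseline-adjusted: D1 − r × D0
- Size of the discrepancy: (1 − r) × D0

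| assumed r | gap 0.1 SD | gap 0.5 SD |
|---|---|---|
| 0.5 | 0.05 | 0.25 |
| 0.6 | 0.04 | 0.20 |
| 0.7 | 0.03 | 0.15 |

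The two estimates agree when D0 = 0, so the match does matter even for a measured variable.

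**4. Measured differences: precision.** If adjusted covariates explain an assumed share R² of group membership, the effective n per group is 385 × (1 − R²), holding residual SD at 1.

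| assumed R² | effective n | power at 0.2 |
|---|---|---|
| 0 | 385 | 79.2% |
| 0.1 | 346.5 | 74.9% |
| 0.2 | 308 | 69.9% |
| 0.3 | 269.5 | 64.1% |
| 0.5 | 192.5 | 50.1% |

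**5. The one-sided exclusion.** The protocol does not say whether any treatment centre is in an area with another intensive initiative, so no bias can be computed. For scale, suppose that one project of 11 equal samples carries an assumed 0.2 to 0.3 SD of extra change from another programme. That project's result moves by the full amount. The national estimate moves by 0.2/11 = 0.018 to 0.3/11 = 0.027 SD.

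**The case against.** The strongest defence is that 9.1.1 gives its reason in terms of measured variables and emphasises the word. Section 4.3 takes a similar position: the comparison is acceptable provided that measured differences are taken into account, and unmeasured ones remain a caveat. A reader might infer that the two sections say flatly opposite things. They do not. The same premise is used in both, but 9.1.1 drops the caveat and draws an unqualified conclusion. The false-positive figures in step 2 bear on that conclusion and not on the premise.

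A reader might infer from footnote 73 that the protocol admits poor comparability here. It reports that mismatch "posed problems in making comparisons between roughly equivalent NESS and MSC groups" in the Sure Start evaluation, and expects NEYAI to avoid this through a close match on the index. That expectation does, however, treat matching as important.

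It would also be too strong to say that matching rests on the deprivation score alone. Centres are matched too. The score is only the one matching variable that is specified.

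On the exclusion, a reader might infer that the Tallaght project is contaminated. Nothing in the protocol places its centres in West Tallaght or in any other excluded area. Effects of earlier investment that are already present at baseline are differenced out of a change comparison, so only a later effect on change would bias it. Nor is exposure beyond control: the exclusion rule presumes that the initiatives are known, and every centre has an ID, so exposure can be coded by centre.

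The gap, r and R² are assumptions, and a 0.1 SD gap does little harm. Step 4 also holds residual variance fixed. Adjusting for baseline at r of 0.5 to 0.7 leaves 1 − r² = 0.75 to 0.51 of the variance, so an effective 270 becomes about 270/0.75 = 360 to 270/0.51 = 530. The loss is real against a well-matched adjusted analysis, and it is a loss of precision, not of identification.

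Finally, balance thresholds, weighting and trimming are commonly left to an analysis plan, and their absence is no fault of this protocol.

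**Conclusion.** The concern stands in two limited parts.

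First, the 9.1.1 conclusion is wrong as written. Adjustment reaches measured differences only, and poor matching can bias or weaken the estimate. The divergence between change and baseline-adjusted results ranges from minor (0.03 to 0.05 SD for a 0.1 SD gap) to as large as the smallest target effect (0.15 to 0.25 SD for a 0.5 SD gap), under an assumed r of 0.5 to 0.7. Which applies will be known only when baseline outcomes are compared.

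Second, the exclusion of areas with other intensive initiatives is one-sided. Its effect is conditional on a treatment centre being in such an area and its size is unknown. If it occurs, it matters mainly for that project's result. Under the assumed 0.2 to 0.3 SD, the national estimate would move by only about 0.02 to 0.03 SD. The documents do not support a finding that the Tallaght result is inflated.

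**What to change.** - Replace the sentence in 9.1.1 with one saying that adjustment addresses measured differences only, and that poor matching can bias or weaken the impact estimate, in line with section 4.3.
- Extend the 9.1.1 comparison to baseline outcomes, reported as standardised differences. The means and SDs planned for Table 2 supply the ingredients.
- Report a baseline-adjusted impact estimate alongside the change comparison.
- Code known other intensive initiatives for every centre in both arms. Re-estimate the national result and any affected project's result with exposed treatment centres left out.

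The cost is a little extra analysis, one centre-level field, and a smaller sample in the sensitivity analysis.
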